6. DATA HANDLING

6.1 Study Data

Study data identified in the schedule of procedures are collected, and source verified, in eCRFs at the site conducting the study. All relevant study data will be formulated into data sets to provide transparency, traceability, and integrity of trial analysis results from collection source.

Observed study data will be mapped to the CDISC Study Data Tabulation Model (SDTM) and serve as the source data from the trial. All study analyses will be completed using analysis data sets that are derived from the SDTM and follow the CDISC Analysis Data Model (ADaM) architecture.

6.1.1 Clinical Data – CDISC Study Data Tabulation Model (SDTM)

Domains will be mapped to CDISC SDTM version 3.2. The SAP will not be amended to provide information on additional SDTM domains. All SDTM domains will be fully documented with define documents (DEFINE.XML) and a study data reviewer's guide (SDRG) after database lock and final analyses are completed.

6.1.2 Analysis Data – CDISC Analysis Data Model (ADaM)

All planned and exploratory analyses will be completed using the ADaM data sets derived from the SDTM domains for this study. Analysis data sets will contain all derived study endpoints required for analysis. All analysis data sets will be fully documented with define documents (DEFINE.XML) and an analysis data reviewer's guide (ADRG) after database lock and final analyses are completed.

Additional analysis data sets may be developed to support unplanned analyses after database lock. The SAP will not be amended for additional analysis data sets defined for the study and these additional data sets will be documented in the define documentation completed after all analyses are completed for the trial and the clinical study report is written.

6.2 Handling of Early Termination Visit Information

If a patient is terminated early from this study the early termination visit data will be analyzed at the closest scheduled visit. If the closest visit has valid data, the early termination data will be assigned to the next available visit.

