4.1. Justification of Route, Dose, Regimen, and Treatment Period

Topical ocular administration of oxymetazoline hydrochloride at lower concentrations (0.01%, 0.025%) results in vasoconstriction and reduction of hyperemia but does not have the pharmacologic effect of improving the superior visual field or increasing the marginal reflex distance (MRD). This effect is present at a concentration of 0.1%, the concentration of RVL-1201, based on the results of the Phase 3 study, Study RVL-1201-201. The pilot study, Study RVL-1201-001, showed that RVL-1201 administered once daily (QD) and twice daily

(BID) was more effective at elevating the upper eyelid than Vehicle, but BID dosing did not result in increased upper eyelid elevation compared to QD dosing. The safety profile of RVL-1201 QD in both studies was satisfactory, with AEs that were mild, and did not require treatment. In the pilot study, slightly more subjects in the BID treatment group than in the QD treatment group reported AEs. These were deciding factors in going forward with QD dosing in the first Phase 3 study. The current Phase 3 study, Study RVL-1201-203 will evaluate the safety of 1 drop of RVL-1201 Ophthalmic Solution in each eye QD for 84 days. This dosing duration was chosen to evaluate the safety of longer-term dosing than the 42-day period evaluated in Study RVL-1201-201.

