10.4. Early Discontinuation Assessment Procedures

If a study subject is discontinued from study medication before Day 84 (Visit 4) and after Day 1 (Visit 1), procedures performed will include the following:

- Collect all opened and unopened study medication materials (opened and unopened unit-dose vials and pouches) from the subject
- Urine pregnancy test (for females of childbearing potential only)
- Concomitant medication review
- AE assessment
- Study medication tolerability assessment (rating by subject)
- BP/HR (taken after 3 minutes at rest)
- Pupil diameter measurement (from external photograph)
- Snellen VA
- SLE
- CFS
- IOP
- Dilated ophthalmoscopy/fundus exam
- Study medication accountability

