11.5. Safety Endpoints

The safety of RVL-1201 compared to Vehicle will be evaluated by the following endpoints:

1. Comparison of ocular and non-ocular AEs by:
 - a. Frequency
 - b. Intensity
 - c. Relationship to treatment
 - d. Serious adverse events
 - e. Adverse events leading to withdrawal of study medication
2. Comparison of subjects with findings on the following measures:
 - a. Slit-lamp examination
 - b. Corneal fluorescein staining
 - c. Pupil diameter
 - d. Dilated ophthalmoscopy/fundus examination
 - e. Tonometry
 - f. Snellen VA (corrected)
 - g. Vital signs (BP/HR)
3. Comparison of tolerability as measured by the tolerability scale.

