8.6 Ophthalmoscopy and Fundus Exam

The status of the fundus with respect to normalcy, non-clinically significant or clinically significant changes will be tabulated (n, %) by visit and treatment group. The summaries will be presented by eye (left eye (OS) and right eye (OD)).

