8.7 Tolerability Assessment

Tolerability assessments will be summarized in frequency tables based on the ordinal scale for each treatment group at the Day 84 assessment.

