12. SCHEDULE OF PROCEDURES

Assessment	Screening/Baseline Randomization Day 1	Day 14 (± 3 Days)	Day 42 (± 3 Days)	Day 84 (± 3 Days)	Early Discontinuation
Visit	1	2	3	4	
Informed consent	X				
Demographics/medical/ocular history	X				
Collect study medication materials		X	X	X	X
Urine pregnancy test ^a	X			X	X
Prior/concomitant medications	X	X	X	X	X
Adverse event assessment ^b	X	X	X	X	X
Tolerability assessment				X	X
Blood pressure/heart rate ^c	X	X	X	X	X
External digital photograph	X	X	X	X	X
Marginal reflex distance (OU) ^d	X				
Pupil diameter measurement (OU) ^d	X	X	X	X	X
Snellen visual acuity (OU) ^e	X	X	X	X	X
Slit lamp exam (OU)	X	X	X	X	X
Corneal fluorescein staining (OU)	X	X	X	X	X
Intraocular pressure tonometry (OU)	X		X	X	X
Dilated ophthalmoscopy/fundus exam (OU) ^f	X			X	X
Review inclusion/exclusion criteria / Randomize eligible participants	X				
Dispense/administer study medication ^g	X	X	X		
Study medication accountability	X	X	X	X	X

MRD = marginal reflex distance; OU = both eyes; VA= Visual acuity

^a Females of childbearing potential only (females who have started their menstrual cycles).

^b For precise timing of adverse events at each visit, please refer to details of each individual visit in Section 10 of the protocol.

^c Resting blood pressure and heart rate are taken seated after 3 minutes rest.

^d MRD and pupil diameter will be measured from the external photograph.

^e If the corrected or uncorrected VA is 20/80 or better, no additional refraction is necessary. If corrected or uncorrected VA is worse than 20/80 an updated refraction must be performed, which must be used for all VA assessments during the study. The subject must wear the same glasses, if applicable, at each visit. For subjects with surgical monovision correction, VA assessment may be conducted in the near vision eye with a near vision reading card held at approximately 14 inches from the subject's eye.

^f Only tropicamide (Mydriacyl) should be used for this exam. Phenylephrine hydrochloride (Neosynephrine) may NOT be used.

^g Study medication will be dispensed at Day 1 (Visit 1), Day 14 (Visit 2), and Day 42 (Visit 3). Study medication will be administered at the study site on Day 1.

Otherwise, study medication will be administered QD in the morning at home daily.

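### SAP 6.2 moves early-exit data to the next free visit at any distance, so Day 84 tables can hold Week 6 readings, and SAP 8.7 leaves early-exit tolerability ratings without a stated place

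*SAP*

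**What the plan says.** SAP 6.2 has two rules. The first puts early-termination data at the scheduled visit closest in time. The second covers the case where that visit is already filled: "If the closest visit has valid data, the early termination data will be assigned to the next available visit". Neither rule sets a maximum distance, and no other SAP section defines an analysis window. The ±3 days in the schedule of procedures governs when visits are held.

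SAP 8.1 to 8.6 and 8.8 summarise the eye examinations and vital signs by visit. For the fundus, SAP 8.6 reads: "The status of the fundus with respect to normalcy, non-clinically significant or clinically significant changes will be tabulated (n, %) by visit". In the SAP 12 schedule this examination is marked only at Day 1, Day 84 and Early Discontinuation.

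Tolerability is one of three endpoint groups in Protocol 11.5: "Comparison of tolerability as measured by the tolerability scale". In the SAP 12 schedule the row "Tolerability assessment" is marked only at Day 84 and Early Discontinuation, and Protocol 10.4 also lists the rating among the early-discontinuation procedures. SAP 8.7 provides one summary: "Tolerability assessments will be summarized in frequency tables based on the ordinal scale for each treatment group at the Day 84 assessment".

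**The concern.** Protocol 4.1 explains the 12-week treatment period: "This dosing duration was chosen to evaluate the safety of longer-term dosing than the 42-day period evaluated in Study RVL-1201-201". The Day 84 rows are where a reader will look for 12-week safety. Followed as written, SAP 6.2 lets those rows include readings taken about six weeks into treatment, from subjects who did not complete it. The values are observed but their time label is wrong, which fits poorly with the observed-case approach of SAP 6.3 and Protocol 11.1.1.

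The disposition table in SAP 7.2 reveals this only indirectly. Comparing the Day 84 n with the number completing Visit 4 shows roughly how many values were moved, but the actual exit days would have to be found in the listings.

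For tolerability the difficulty is ambiguity. SAP 6.2 does not say whether a visit counts as filled as a whole or separately for each assessment. Two programmers could produce different tolerability tables from the same SAP. The subjects in question include any who left because of discomfort, whose ratings matter most.

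**Working it through.** **Inputs.** Post-baseline visits are on Days 14, 42 and 84 (SAP 2.5), each ±3 days (SAP 12). Early-discontinuation procedures apply after Day 1 and before Day 84 (Protocol 10.4). Planned arms are 150 and 75 (SAP 2.6). The plan states no figure to reproduce.

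**Midpoints.** (14 + 42)/2 = Day 28 and (42 + 84)/2 = Day 63.

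**Rule applied to each exit day.** Earlier visits are taken as attended on their nominal days. The Day 84 rows below hold for pupil diameter, visual acuity, slit lamp, corneal staining, IOP, blood pressure and heart rate. The Day 42 rows hold for the same list without IOP, which is not scheduled at Visit 2.

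| Exit day | Nearest visit | Tabulated as | Days early |
|---|---|---|---|
| 15–27 | Day 14 (filled) | Day 42, by the second rule | 15–27 |
| 28 | tie; Day 14 filled | Day 42 | 14 |
| 29–41 | Day 42 | Day 42, by the first rule | 1–13 |
| 43–62 | Day 42 (filled) | Day 84, by the second rule | 22–41 |
| 63 | tie; Day 42 filled | Day 84 | 21 |
| 64–83 | Day 84 | Day 84, by the first rule | 1–20 |

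- Day 84 receives 20 + 1 + 20 = 41 exit days. Only Days 81 to 83 are within ±3, so 41 − 3 = 38 are outside: 20 + 1 through the filled-visit rule or the tie, and 17 through nearest-visit mapping.
- Day 42 receives 27 exit days, of which 27 − 3 = 24 are outside ±3.
- Using the visit windows: with Visit 3 on Day 39, an exit on Day 40 becomes Day 84, which is 84 − 40 = 44 days early. With Visit 2 on Day 11, an exit on Day 12 becomes Day 42, which is 42 − 12 = 30 days early.

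**Tolerability.** Days 2 to 83 are 82 days. Removing Days 14 and 42 leaves 80 non-visit exit days.

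| Reading of SAP 6.2 | Omitted from the Day 84 table | Labelled Day 84 |
|---|---|---|
| Whole visits are moved | Days 2–41: 40 − 1 = 39 of 80 | Days 43–83 |
| Visit chosen by date, validity checked per assessment | Days 2–62: 61 − 2 = 59 of 80; Day 63 tied | Days 64–83 |
| Only visits where the assessment is scheduled count | none | all 80; a Day 2 exit is 84 − 2 = 82 days early; 80 − 3 = 77 outside ±3 |

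The third reading has the same effect on the fundus examination, whose only scheduled post-baseline visit is Day 84.

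**Possible number of subjects.** The documents give no exit rate. As an assumption, let a proportion p of 5% to 20% leave, spread evenly over Days 2 to 83. Expected exits on Days 43 to 62 are n × p × 20/82:

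- RVL-1201: 150 × 0.05 × 20/82 = 1.8, up to 150 × 0.20 × 20/82 = 7.3.
- Vehicle: 75 × 0.05 × 20/82 = 0.9, up to 75 × 0.20 × 20/82 = 3.7.

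As a share of the Day 84 n, taken as n(1 − p) + n × p × 41/82, this is 1.8/(142.5 + 3.75) = 1.3% at p = 5% and 7.3/(120 + 15) = 5.4% at p = 20%.

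In the categorical tables one subject is 1/150 = 0.67 points for RVL-1201 and 1/75 = 1.33 points for Vehicle at planned N. Each is slightly more once dropouts leave the denominator.

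**The case against.** The strongest reply is that the effect is small and the labelling only loose. With Visit 3 on its nominal day, every moved reading for the assessments listed still comes from after Day 42, so the extended-exposure question is not lost. Of the 38 Day 84 exit days outside ±3, 17 arrive by ordinary nearest-visit mapping, which many plans use. Counts of calendar days are not counts of subjects: Protocol 8.5 encourages subjects who stop the drug to keep attending, and an early-discontinuation assessment may fall on a scheduled visit. No direction of bias is shown. There are no tests (Protocol 11.1), all data are listed (SAP 7.1), and discomfort recorded as an adverse event that ended treatment still appears under SAP 8.9. For tolerability, Day 84 is the only scheduled visit with that rating, so a reader might naturally place early ratings there, and the table is fully specified for everyone rated at Day 84.

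Most of this stands as a limit on size. It does not make the labels right. In a study whose whole output is descriptive tables, the visit label carries the message. The natural reading for tolerability is also the one that can call a Day 2 rating Day 84. How strict the window should be is a matter of judgement; ±3 days is used here because it is already the protocol's own visit window.

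**Conclusion.** The concern holds in both parts. Followed exactly, SAP 6.2 can put readings from Day 43 (Day 40 if Visit 3 was early) into Day 84 rows, up to 41 days early (44 with an early Visit 3). For tolerability, each reading of SAP 6.2 omits some early-exit ratings, labels some as Day 84 well before that day, or does both.

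The day counts rest on earlier visits having been attended on schedule, except where the window is varied. The number of subjects is unknown; the 1.3% to 5.4% share of the Day 84 n rests entirely on the assumed exit rates and their even spread. The adverse event summaries are unaffected. This should be corrected before database lock, but it does not threaten the study as a whole.

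**What to change.** Replace the allocation rule in SAP 6.2 with wording such as:

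> Separately for each assessment, early-termination data are used at a scheduled visit only if that assessment is scheduled at that visit, the data were taken within that visit's ±3-day window, and no scheduled value exists. All other early-termination data are shown in a separate Early Discontinuation row.

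In SAP 8.7, tabulate each Safety subject's final tolerability rating, from Day 84 or Early Discontinuation (if both exist, the one nearer the last dose), and keep the Day 84-only table as supportive.

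Trying the rule on examples:

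- An exit on Day 16 after Visit 2, or on Day 43 after Visit 3, goes wholly to the Early Discontinuation row.
- An exit on Day 40 without Visit 3 uses Day 42 for the assessments scheduled there; fundus and tolerability go to the Early Discontinuation row.
- An exit on Day 82 uses Day 84 throughout.

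The cost is SAP wording and a few table rows. Protocol 10.4 already collects the data. The n at Days 42 and 84 falls slightly, and the Day 84 row moves closer to completers only, which a footnote should say. The Early Discontinuation row and the final-rating table pool different lengths of exposure. The change does not deal with scheduled visits held out of window, or with subjects who stop the drug but keep attending.

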Each subsequent morning of dosing, the subject will open a pouch from the box, administer one full drop to each eye from a single new unit-dose vial and close the eyes gently for 30 seconds, empty the remaining contents of the unit-dose vial, then store the opened vial in the foil pouch, and place it in the box for return to the study site. On Day 14 ± 3 days (Visit 2), subjects will return all opened and unopened study medication materials (the box, pouches, and unit-dose vials), and site personnel will conduct study medication accountability procedures and dispense study medication for the next study period. On Day 42 ± 3 days (Visit 3) all study medication materials will be returned to the study site, study medication accountability will be conducted, and study medication for the remaining study period will be dispensed. Lastly, on Day 84 ± 3 days (Visit 4) all study medication materials will be returned to the study site and final study medication accountability will be conducted. The Day 84 visit will be the last day of study treatment; no further study medication will be dispensed at this visit.

Note: Contact lens wear is permitted during the study. Contact lenses must be removed prior to instillation of study medication and must not be reinserted for at least 15 minutes after study medication instillation. Contact lenses must not be worn during study visits.

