11.1.1. Handling of Missing Data

No missing data will be imputed. The reasons for missing data will be recorded in the eCRF.

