2.5 Study Plan/Procedures

This will be a Phase 3, randomized, multicenter, double-masked, placebo-controlled study to evaluate the extended safety of RVL-1201 Ophthalmic Solution compared to Vehicle (placebo) for the treatment of acquired ptosis. The study will be conducted over 84 days (12 weeks).

Eligible subjects will be randomized in a 2:1 ratio to one of 2 treatment arms and treated for 84 days:

- RVL-1201 Ophthalmic Solution 1 drop in each eye QD in the morning (N = 150)
- Vehicle (placebo) 1 drop in each eye QD in the morning (N = 75)

Both eyes will be treated and assessed.

Following screening evaluations at the Screening/Baseline visit (Day 1), a determination of eligibility will be made, and eligible subjects will be randomized and receive study medication.

Study medication, RVL-1201 or Vehicle (placebo), will be provided in identical-appearing unit-dose vials. The identity of the study medications will be masked to the subject, Investigator, study personnel responsible for ophthalmic evaluations, and Sponsor personnel.

Subjects (or their caregiver, if necessary) will administer study medication QD in the morning during the study period.

Safety follow-up visits will be conducted at Day 14 (Visit 2), Day 42 (Visit 3), and Day 84 (Visit 4).

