6.3 Handling of Missing Data

All analyses will be based on observed cases (without imputation).

If the intensity of an AE is missing, the event will be considered severe. If relationship of the AE to study drug is missing, the event will be counted as related.

Adverse events will be considered treatment emergent unless it can be determined from the onset or end date information that the event cannot have been treatment emergent.

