7. STATISTICAL ANALYSIS

7.1 General Considerations

This is a Phase 3 study to evaluate the safety of daily treatment with RVL-1201 Ophthalmic Solution (oxymetazoline hydrochloride ophthalmic solution, 0.1%) compared to Vehicle (placebo) for the treatment of acquired ptosis over an extended dosing period of 12 weeks.

Subjects will be randomized in a 2:1 ratio of RVL-1201 Ophthalmic Solution to Vehicle into 2 treatment groups and treated for 84 days:

- RVL-1201 Ophthalmic Solution 1 drop in each eye QD in the morning (N = 150)
- Vehicle (placebo) 1 drop in each eye QD in the morning (N = 75)

Descriptive statistics will be used to summarize continuous outcomes (number of subjects [N], mean, standard deviation or standard error of the mean, median, maximum, and minimum) and categorical variables (frequency and percentage) at each assessment time point.

All data collected in the study database will be presented in the listings.

All statistical analyses and reporting will be performed using the SAS® System Version 9.4 or later.

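### SAP 6.2 assigns early-termination readings to a scheduled visit with no limit on the gap in days, so a reading from as early as Day 43 can be tabulated as Day 84

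*SAP*

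**What the plan says.** SAP 6.2 has two steps. First: "If a patient is terminated early from this study the early termination visit data will be analyzed at the closest scheduled visit". Second: "If the closest visit has valid data, the early termination data will be assigned to the next available visit". It gives no maximum gap, no rule for ties and no separate row for early-termination data.

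The post-baseline visits are Days 14, 42 and 84, each with a window of ±3 days (Protocol 6.1, Table 2; SAP 12). SAP 7.1 promises continuous summaries, including minimum and maximum, and "categorical variables (frequency and percentage) at each assessment time point". SAP 8.1 to 8.6 and 8.8 tabulate IOP, visual acuity, pupil diameter, corneal staining, slit lamp, fundus and vital signs by visit.

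On missing data, Protocol 11.1.1 says "No missing data will be imputed", and SAP 6.3 says "All analyses will be based on observed cases (without imputation".

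On the purpose of 12 weeks, Protocol 4.1 says: "This dosing duration was chosen to evaluate the safety of longer-term dosing than the 42-day period evaluated in Study RVL-1201-201".

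**The concern.** A subject who leaves soon after attending a visit already has data at the closest visit, so the second step moves the exit reading forward to a visit the subject never reached. The first step can also place a reading well ahead of its true day.

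The Day 84 row is the only by-visit evidence on dosing beyond 42 days, which is why this trial was given its length. Under SAP 6.2 that row can mix 12-week readings with readings taken after little more than six weeks. Because minimum and maximum are reported, a single mis-dated reading can become the reported 12-week extreme. A clinically significant finding at an exit on Day 43 would be counted as a Day 84 finding.

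**Working it through.** There is no planned figure to reproduce: the sample size is not calculated and no tests are planned. The check is to apply the two steps to every possible exit day from 2 to 83.

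**Measures taken at every visit** (visual acuity, pupil diameter, slit lamp, corneal staining, BP/HR), with earlier visits attended on Days 14 and 42:

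| Exit day | Closest visit | Already filled? | Reported as | Days ahead |
|---|---|---|---|---|
| 15-27 | 14 | yes | 42 | 42 − 27 = 15 to 42 − 15 = 27 |
| 28 | tie, 14 or 42 | – | 42 either way | 14 |
| 29-38 | 42 | no | 42 | 4 to 13 |
| 39-42 | 42 | no | 42 | within ±3 |
| 43-62 | 42 | yes | 84 | 84 − 62 = 22 to 84 − 43 = 41 |
| 63 | tie, 42 or 84 | – | 84 either way | 21 |
| 64-80 | 84 | no | 84 | 4 to 20 |
| 81-83 | 84 | no | 84 | within ±3 |

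- Day 42 row: 28 exit days (15-42) feed it, and 24 (15-38) are outside the window.
- Day 84 row: 41 exit days (43-83) feed it, and 38 (43-80) are outside the window. Of those 38, 20 come through the second step (21 if the Day 63 tie goes to Day 42) and the rest through the uncapped first step.

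**Measures taken at fewer visits.** IOP is not scheduled at Day 14. The fundus exam is not scheduled at Day 14 or Day 42. SAP 6.2 does not say whether the closest visit, and the presence of valid data, are judged for the visit as a whole or for each measure.

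- Closest visit judged overall: an exit on Day 10 puts IOP in the Day 14 column, and an exit on Day 30 puts the fundus reading in the Day 42 column. Neither exam is scheduled there.
- Closest visit overall, valid data per measure: a fundus reading on Day 43 stays at Day 42, because no fundus result fills that visit.
- Both judged per measure: IOP from Day 2 onward can be reported as Day 42, and a fundus reading from Day 2 onward as Day 84.

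Tolerability is collected at Day 84 and at early discontinuation (SAP 12) and tabulated at Day 84 (SAP 8.7). Read per measure, it behaves like the fundus exam.

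**Illustrative size.** The documents give no dropout rate. Assume a fraction *p* leaves early, spread evenly over the 82 days from Day 2 to Day 83.

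- Day 84 row, as a fraction of the arm: (1 − p) + p × 41/82
- Out-of-window part: p × 38/82
- Part through the second step: p × 20/82

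| p | Row | Out of window | Share | Second-step share |
|---|---|---|---|---|
| 5% | 0.975 | 0.0232 | 2.4% | 0.0122/0.975 = 1.3% |
| 15% | 0.925 | 0.0695 | 7.5% | 0.0366/0.925 = 4.0% |

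In subjects, with 150 and 75 planned, p × N × 38/82 gives 3.5 to 10.4 in the active arm and 1.7 to 5.2 in vehicle.

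**The case against.** **This is visit assignment, not imputation.** Each early-termination value is a real observation, used once. Nothing is created or duplicated, and SAP 6.2 and 6.3 are separate rules. This stands. A reader might infer that SAP 6.2 breaches the no-imputation statements, but the wording does not support that. What remains is a tension of effect: the rule fills a Day 42 or Day 84 cell that was never observed for that subject, which is hard to square with an observed-cases table for that day.

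**The consequences are limited and partly visible.** No tests are planned (Protocol 11.1), treatment-emergent AE tables are not built by visit (SAP 8.9), and all data are listed (SAP 7.1). Disposition shows how many subjects complete each visit (SAP 7.2), so a Day 84 n above the number of Visit 4 completers would be noticeable. Protocol 8.5 also asks sites to keep subjects attending after they stop medication, which reduces the number of such readings. All of this stands and keeps the point modest. It does not make the affected rows correct, and a surplus in n does not tell the reader which values are mis-dated.

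**Early leavers need not have had a problem.** Protocol 7.3 allows withdrawal for any reason, while Protocol 8.5 names adverse events as a ground for stopping medication. The misplacement may therefore be related to safety findings, but the documents do not show that it is.

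**Conclusion.** The point holds for the by-visit descriptive tables. Followed exactly, SAP 6.2 reports exits from Days 43-62 as Day 84 through its second step and exits from Days 64-80 through its first, assuming earlier visits were attended on nominal days. The ties at Days 28 and 63 are unresolved in the text but do not change the destination under that assumption. The 2.4-7.5% share of the Day 84 row rests on assumed 5-15% early termination, spread evenly.

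Three stronger readings are not supported:

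- That 5-15% of Day 84 readings are mis-dated. This would need that whole share of subjects to leave after Visit 3 and every one of them to contribute an out-of-window reading. The documents give neither a rate nor a timing.
- That IOP and fundus readings necessarily land in columns where the exam is not scheduled. This follows if the closest visit is judged overall. Judged entirely per measure, they land in scheduled columns but far from their true day. The text does not choose.
- That tolerability is certainly affected, or certainly not. It depends on the same unresolved choice.

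The rule should be corrected because it blurs exposure in the one by-visit row that addresses dosing beyond 42 days. It does not undermine the AE analysis.

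**What to change.** Replace SAP 6.2 with:

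> Early-termination data are assigned to a scheduled visit only if they fall within that visit's ±3-day window, the measure is scheduled at that visit, and the subject has no valid data for that measure there. Otherwise they are tabulated by treatment group in a separate Early Discontinuation row, with study day listed.

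For measures scheduled at Day 84, only exits on Days 81-83 would then enter the Day 84 row. State in SAP 8.7 that tolerability follows the same rule. Optionally, add a last on-treatment assessment row, so that each subject in the Safety population with a post-baseline value is represented once.

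The cost is SAP wording, one or two extra rows per table, and a slightly smaller n at Day 42 and Day 84. No data collection or study procedure changes.
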